First, all patients with NVAF who are newly diagnosed and initiated apixaban or warfarin will be extracted from the database. Among these patients, patients with at least one predetermined high bleeding risks will be extracted. In this study, predetermined high bleeding risks are 1) patients with hypertension diagnosis, 2) patients with liver dysfunction, 3) patients with renal dysfunction diagnosis, 4) patients with a history of bleeding, 5) patients with hemorrhagic stroke, 6) patients with alcohol abuse, 7) patients with concomitant used of antiplatelet drugs, 8) patients with chronic (continuously for longer than 90 days) concomitant use of Non-steroidal antiinflammatory drug (NSAID), 9) highly elderly (> 80 years old), 10) patients with refractory hypertension, 11) patients with a history of peptic ulcer diagnosis, 12) patients with active cancer, 13) patients with diabetes mellitus, 14) patients whose body weight is <40kg, 15) patients with polypharmacy (sea Section 5.4 for the definition). Patients with at least one predetermined high bleeding risk factor will be divided into two cohorts, apixaban and warfarin cohorts, based on the first prescribed drug just after the NVAF diagnosis. Patient characteristics will be balanced by using an inverse probability of treatment weighting (IPTW) method to create balanced apixaban and balanced warfarin cohorts. Comparisons will be conducted by using these balanced warfarin and apixaban cohorts (Kaplan-meier curves, incidence rates per 1,000 person-year and hazard ratio with 95% confident intervals). The primary safety and effectiveness analyses are comparison of apixaban with warfarin in patients with at least one predetermined risk factor for bleeding.

- Second, after the first analysis, we will conduct separate interaction analysis of the treatment (apixaban vs. warfarin) and one of the 15 risk factors (e.g., hypertension yes vs no, etc) to see if treatment effects are consistent among patients with or without each specific factor
- Third, patients will be stratified by risk factors into 15 subgroups, and same IPTW analyses as described in the step 1 will be conducted only in the subgroups with adequate sample sizes.

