3.2. STATISTICAL DECISION RULES

For primary safety and effectiveness analyses, all statistical tests will be performed at p=0.05 (twosided) with no adjustment for multiplicity. Since we will conduct various multiple subgroup analyses, which lead to the "Multiple Testing Problem". Here these subgroup analyses will be conducted with an exploratory purpose and we do not plan to conclude anything from the results here. Therefore, we will not adjust the p values and still the use p<0.05 to indicate the statistical significance.

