7. STATISTICAL METHODOLOGY AND STATISTICAL ANALYSES

7.1. STATISTICAL METHODS

7.1.1. Calculation of Propensity Score

In this study, balanced cohorts (apixaban vs. warfarin) will be created by an IPTW method. Propensity scores will be estimated by unconditional logistic regression analyses that incorporate potential predictors of therapy as independent variables in the regression and cohort status as the outcome. Using calculated propensity score an IPTW method will be applied to balance the warfarin and apixaban cohorts, which will be used for the comparisons of all endpoints (sections 5.1 and 5.2). The following covariates will be included in the logistic regression for calculation of propensity score:

• age on index date

- gender
- CHADS2 score in baseline
- CHA2DS2-VASc score in baseline
- heart failure diagnosis in baseline
- coronary heart disease diagnosis in baseline
- peripheral arterial disorder diagnosis in baseline
- myocardial infarction diagnosis in baseline
- hyperthyroidism or thyrotoxicosis in baseline
- TIA diagnosis in baseline
- stroke or SE diagnosis in baseline
- renal dysfunction diagnosis in baseline
- liver dysfunction diagnosis in baseline
- bleeding diagnosis in baseline
- hypertension diagnosis in baseline
- diabetes mellitus diagnosis in baseline
- treated with antiplatelet drug in baseline
- treated with NSAIDs in baseline
- treated with gastric secretion inhibitor in baseline
- treated with statin-based drug in baseline
- treated with anti-hypertensives in baseline
- treated with anti-arrhythmics in baseline
- treated with beta-blockers in baseline
- treated with heparins in baseline
- cardioversion in baseline

The operational definitions for the above covariates are shown in the Section 5.4.

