7.1.6. Cox proportional hazards model

Cox proportional hazards model will be used to compare endpoints (time-to-endpoint) in the propensity-score-weighted cohorts with robust sandwich estimates to account for the potential clustering within weighted sets. The Cox proportional hazards model will include only index OAC treatment as the independent variable if patient characteristics are balanced between groups... If not balanced, the unbalanced variable will be also included to the model in addition to the index OAC PFIZER CONFIDENTIAL

treatment. The hazard ratios with corresponding 95% confidence intervals and p-values will be reported.

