7.1.9. Power calculation

Incidence rates of stroke/SE and major bleeding in the primary analysis population here (that is, de novo NVAF patients initiating an anticoagulant therapy with warfarin or apixaban who have at least one bleeding risk factor) have not been investigated yet and hazard ratios of stroke/SE and major bleeding in apixaban users relative to warfarin users also have not been investigated yet. Therefore, we estimated the needed sample size to achieve adequate statistical power (e.g., 0.80) based on the major previous RCT and RWE conducted so far.

Study	Subgroup	HR	Incidence rate (%/year)	
			Warfarin	Apixaban
ARISTOTLE	-	0.79	1.60	1.27
	≥ 75 years		2.2	1.6
	≤ 60kg		3.2 2.0	
	Prior stroke or TIA		3.2 2.5	
	Diabetes		1.9	1.4
	Severe to moderate renal dysfunction		2.7	2.1
	Aspirin		1.9 1.3	
CER3		0.66	2.87	1.55

Stroke/SE

≥ 80 years	4.04	2.06
< 60 kg	3.47	2.45
Severe to moderate renal dysfunction	2.50	1.33
Anti-platelet	3.61	1.93

Major bleeding

Study	Subgroup	HR		nce rate year)
			Warfarin	Apixaban
ARISTOTLE	-	0.69	3.09	2.13
	≥ 75 years		5.2	3.3
	≤ 60kg		3.0	2.1
	Prior stroke or TIA		3.9	2.8
	Diabetes 3.1		3.1	3.0
	Severe to moderate renal dysfunction		6.4	3.2
	Aspirin		3.7	2.7
CER3		0.74	2.81	1.69
	≥ 80 years		3.94	2.35
	< 60 kg		3.67	2.61
	Severe to moderate renal dysfunction		3.32	2.21
	Anti-platelets		3.07	1.91

As shown in Tables above, absolute incidence rates of stroke/SE and major bleeding could be higher in patients with (a) risk factor(s) associated with bleeding. However, the ARISTOTLE study has revealed that P-value for interaction was mostly >0.05 and relative risk (HR) may not be changed in the specific subgroups compared to the entire cohorts

Based on the incidence rates and HRs shown above, sample size required for adequate statistical power (e.g., power=0.8) was estimated as follows,

Sample size calculation

	Assumption: Values used for calculation	Calculated results
For major bleeding		
Type I error rate	0.05	
Type II error rate	0.2	
Hazard ratio*	0.7	
N ratio in apixaban and warfarin cohorts	1:1	
Event rate for warfarin	3.77%/year**	
Event rate for apixaban	3.77%/year** 2.50%/year**	
Total events needed		246***
Estimated number of patients		7,846
	PFIZER CONFIDENTIAL	

Page 20 of 56

For Stroke/SE		
Type I error rate	0.05	
Type II error rate	0.2	
Hazard ratio*	0.7	
N ratio in apixaban and	1:1	
warfarin cohorts		
Event rate for warfarin	2.77%/year**	
Event rate for apixaban	2.77%/year** 1.79%/year**	

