Total events needed		246***
Estimated number of patients		10,789
* estimated from ARISTOTLE and CER studies		

** averages of incidence rates shown in the Tables above

*** Calculated using an on-line calculator (Sample Size Survival Analysis (quesgen.com))

In the preliminary check to examine the feasibility of this study, we have obtained that the number of apixaban users and of warfarin users who were eligible for this study were both more than 10,000 patients. Considering that IPTW will be applied to balance the patient characteristics in this study, the number of patients eligible for this study would be adequate for the primary analysis.

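### The propensity model has no term for five of the 15 bleeding-risk factors that define the primary population (active cancer, peptic ulcer, polypharmacy, low body weight, alcohol abuse), so measured confounding can remain in the primary hazard ratios

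*SAP*

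**What the plan says.** SAP 2.1 defines the primary population as patients with at least one of 15 predetermined bleeding risks. The last four are "12) patients with active cancer, 13) patients with diabetes mellitus, 14) patients whose body weight is <40kg, 15) patients with polypharmacy". Peptic ulcer history and alcohol abuse are also among the 15.

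SAP 7.1.1 states "The following covariates will be included in the logistic regression for calculation of propensity score" and gives a closed list of 25 terms. The weights from this model serve every endpoint comparison.

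SAP 7.1.2 assesses the balance of baseline covariates after weighting and treats a standardized difference below 10% as balanced. SAP 7.1.6 fits a Cox model with treatment alone, with one repair: "If not balanced, the unbalanced variable will be also included to the model in addition to the index OAC" treatment.

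SAP 5.4 collects every one of the 15 factors. It labels cancer both a baseline characteristic and a sub-group identifier. Peptic ulcer, polypharmacy, weight below 40 kg and alcohol abuse are labelled sub-group identifier only. Body weight (60 kg cut), eGFR and serum creatinine are labelled baseline characteristics, and none of them is in the 7.1.1 list.

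**The concern.** The plan selects these factors because it regards them as raising bleeding risk, and both the Protocol and SAP rationales name active cancer. A prescriber can often see them when choosing between apixaban and warfarin. A factor that affects both drug choice and outcome, and that is left out of the weights, can leave confounding in the comparison. Here the omitted factors are ones the study was set up to examine, and the data are already in hand.

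The other safeguards do not address this. The E-values in SAP 7.1.8 concern unmeasured confounders. The limitation in Protocol 9.9 concerns background differences that are neither in the database nor in the score, whereas these factors are in the database.

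The SAP states no principle for the omission. Cancer is the only diagnosis labelled a baseline characteristic in SAP 5.4 that 7.1.1 leaves out. Renal dysfunction carries only the sub-group label in SAP 5.4, yet it is in the model.

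**Working it through.** **Coverage of the 15 factors by the 25 terms**

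- Represented (8): hypertension, liver dysfunction, renal dysfunction, bleeding history, antiplatelet use (as any use), NSAID use (as any use), age, diabetes.
- Indirect only (2): hemorrhagic stroke (inside the stroke/SE and bleeding terms) and refractory hypertension (through hypertension, anti-hypertensives and beta-blockers).
- Absent (5): active cancer, peptic ulcer, polypharmacy, body weight below 40 kg, alcohol abuse.

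**The plan's own figures, as a yardstick for precision**

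Inputs from SAP 3.2 and 7.1.9: two-sided alpha 0.05, power 0.80, hazard ratio 0.7, allocation 1:1.

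- Events = 4(1.960 + 0.842)² / (ln 0.7)² = 246.8, against 246 stated.
- Patients, major bleeding: mean rate (3.77% + 2.50%)/2 = 3.135% per year; 246/0.03135 = 7,847, against 7,846 stated.
- Patients, stroke/SE: mean rate (2.77% + 1.79%)/2 = 2.28% per year; 246/0.0228 = 10,789, as stated.

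These figures reproduce and do not depend on the covariate list. At 246 events and HR 0.70 the 95% CI is 0.70 × exp(±1.96 × 2/√246) = 0.55 to 0.90. A bias factor of 1/0.899 = 1.11 equals the distance from the upper limit to 1.

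**Bias that can pass under the 10% rule**

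The documents give no prevalence, imbalance or outcome effect for the omitted factors, so all the inputs here are assumptions. With prevalence p1 in one arm and p2 in the other, and outcome risk ratio RR, the bias factor is [1 + p2(RR − 1)] / [1 + p1(RR − 1)]. p2 is set so that the standardized difference is 0.099.

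| p1 | p2 | RR 1.5 | RR 2 |
|---|---|---|---|
| 0.05 | 0.074 | 1.012 | 1.023 |
| 0.10 | 0.132 | 1.015 | 1.029 |
| 0.15 | 0.187 | 1.017 | 1.032 |
| 0.30 | 0.346 | 1.020 | 1.036 |

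- One factor: about 1-4%.
- All four in the same direction: product 1.066 (RR 1.5) to 1.125 (RR 2). A true HR of 0.70 would read 0.70/1.066 = 0.66 to 0.70/1.125 = 0.62, or, with the opposite imbalance, 0.75 to 0.79.
- Two in each direction at RR 2: net bias of 0.3% to 1.6%, depending on the pairing.

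**Effect of including the factor**

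A simulation of 2,000,000 patients (one factor, prevalence about 18%, outcome HR 2, true HR 0.70) compared weights with and without it. With the factor omitted, the ratio was 0.66-0.67 and the residual standardized difference 0.11-0.20. With the factor included, the ratio was 0.69-0.71 and the difference 0.00. An imbalance of 0.11-0.20 would trigger the 7.1.6 repair, but only for a factor that is checked.

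**The case against.** The strongest case against has four parts.

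1. *The back-stop may already cover these factors.* A reader might infer from the sub-group label that peptic ulcer, polypharmacy, low weight and alcohol abuse are excluded from the balance check. The documents do not support that. Section 5.4 is the covariates section, 7.1.2 speaks of baseline covariates generally, the summary table in 7.2.3 refers the Cox covariates to 5.4, and renal dysfunction carries the same label yet is modelled. Cancer, body weight and eGFR are baseline characteristics and so fall within the check. What stands is an ambiguity for the other factors, and the fact that the repair does nothing below 10%.

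2. *Proxies absorb part of the bias.* Gastric secretion inhibitor and bleeding terms partly carry peptic ulcer. Eight drug-class terms partly carry polypharmacy. The liver dysfunction codes share K70 codes with alcohol abuse. This is fair, and it reduces the problem without removing it. It also rules out counting hemorrhagic stroke or refractory hypertension as wholly uncovered.

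3. *The size is speculative.* A reader might infer a bias of 6.6-12.5%, or one that favours apixaban. Neither follows: the range needs four factors all just under the threshold and all aligned, and the direction reverses if a factor is commoner among apixaban users.

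4. *Both endpoints are not equally exposed.* A reader might extend the same bias to stroke/SE. The plan presents these as bleeding risks and does not say that, for example, peptic ulcer or polypharmacy raises stroke/SE risk by 1.5 to 2 times. The argument is most plausible for major bleeding.

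Alcohol abuse is also uncommon: feasibility found fewer than 2,000 such patients (SAP 2.2.4), against more than 10,000 eligible in each arm (SAP 7.1.9).

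**Conclusion.** The omission is a fact of the text: five of the 15 population-defining factors have no propensity term and two are covered only indirectly, although all are measured. Measured confounding can therefore remain in the primary hazard ratios, most plausibly for major bleeding.

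Its size and direction cannot be derived from the documents. Under the assumptions shown, 1-4% per factor is the reasonable range below the threshold, and 6.6-12.5% is an upper-end illustration. Against a planned upper confidence limit of about 0.90, the low end would seldom change a conclusion; the top of the range could. A factor that is never checked for balance has no such limit.

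This is a should-fix: bias that existing data can reduce, with partial safeguards already in place.

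**What to change.** 1. Correct the cancer definition in SAP 5.4, which currently cites diabetes mellitus codes, and reconcile the 10.3.1 code list, which includes D10-D36, with the term active cancer. Until then the variable cannot be added: as written in 5.4 it would duplicate diabetes.
2. Add active cancer, peptic ulcer, polypharmacy and, where numbers allow, alcohol abuse to the 7.1.1 model.
3. Put all 15 risk factors, body weight and eGFR in the before- and after-weighting balance table, and state that the 7.1.6 rule applies to each of them.
4. Bring in body weight and eGFR through categories with a not-recorded level, or in an expanded-model sensitivity analysis, so that SAP section 6, which drops patients without all required data, excludes no one because of them.

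The cost is SAP wording, a code-list correction and a few more logistic terms. Weights may become slightly more variable, and the not-recorded level brings its own missing-data assumption for weight and eGFR.

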7.1.2. Inverse probability treatment weighting (IPTW)

IPTW with stabilized weights will be used to balance patient characteristics between two groups using propensity score calculated by using a multivariable logistic model as mentioned above (see above 7.1.2.1). However, if a treated patient has a very low propensity score, a very large weight can be created, which leads to increased variability of the estimated treatment effect. In order to address this, the weights can be stabilized by using a formula shown below, by multiplying the treatment and control weights by a constant, equal to the expected value of being in the treatment or comparison cohorts, respectively.

 $W_i = \frac{Z}{PS_i} + \frac{1-Z}{1-PS_i}$, z: probability of treatment without considering covariates

The distribution of the stabilized weight will be reviewed. If there are extreme outliers, the large weights could be set to a less extreme value (e.g. recoding all weights that are outside 5th and 95th percentile). If needed, truncation can be done after stabilizing the weights. After the weights are applied, the balance of the baseline covariates will be assessed. First, the means and proportions of baseline variables are compared. The standardized difference compares the difference in means in units of the standard deviation. If the standardized difference is less than 10%, the covariates are considered balanced.

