9.5. Study size

All eligible patients are extracted from the database and used for the analysis. In the previous study (CER3; conducted based on the data from March 1st, 2011 to July 31st, 2018 for apixaban, dabigatran, edoxaban, rivaroxaban and warfarin), 15,902 patients on warfarin, 22,336 patients on apixaban were eligible for the analysis. The required number of patients for the planned analysis and the estimated number of eligible patients for each cohort is shown in a SAP.

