9.8. Quality control

This study is a retrospective analytical study using quality controlled data in a pre-existing database, and primary data collection will not be conducted. As for the data provided, quality of the data is guaranteed by MDV Co. Ltd., which has professional teams specialized in the maintenance and improvement of data quality. All of these processes are consistently managed in-house. All of operations for data management in MDV Co. Ltd. are conducted in accordance with standard operational procedures of MDV Co. Ltd..

Data analysis will be conducted by Macromill Carenet, Inc. (Tokyo, Japan). The final results will be quality checked internally by Macromill Carenet according to their internal procedures. For quality assurance of analysis, they will conduct code review of all modules of program, descriptive statistics review of all variables and patients row data examination of all output results in a test phase.

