7.1.3. Analysis of Continuous Data

Continuous data will be summarized using descriptive statistics, including the mean, standard deviation, median, first and third quartiles, and minimum and maximum. Baseline characteristics (before and after IPTW weighting) will be compared between patients treated with warfarin and patients treated with apixaban, using the standardized difference.

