7.1.5. Kaplan-Meier Method

For each endpoint, Kaplan-Meier curves will be plotted for the time from the index date to first event by index OAC treatment in each of the propensity-score-weighted cohorts. The log-rank test will be used for comparison between two curves.

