10.2. APPENDIX 2: ADDITIONAL STATISTICAL METHODOLOGY DETAILS

Not applicable

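### The stabilized IPTW formula in SAP 7.1.2 has no treatment indicator; coded as printed, it would leave the cohorts about as unbalanced as before weighting

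*SAP*

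**What the plan says.** SAP 7.1.2 plans stabilized inverse probability weights built from the logistic propensity score of SAP 7.1.1. It describes stabilization in words, "by multiplying the treatment and control weights by a constant, equal to the expected value of being in the treatment or comparison cohorts, respectively", and then prints

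`W_i = Z/PS_i + (1-Z)/(1-PS_i)`

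with the legend "z: probability of treatment without considering covariates". No symbol for the patient's own treatment is defined.

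Nothing else in the documents supplies the formula. SAP 7.1.1 and the protocol contain none, and SAP 10.2, headed "APPENDIX 2: ADDITIONAL STATISTICAL METHODOLOGY DETAILS", is marked as not applicable. The cross-reference in SAP 7.1.2 to a section 7.1.2.1 points to nothing in the SAP text.

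Several later steps bear on the consequences:

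- **Balance.** SAP 7.1.2 plans a review of the weight distribution, possible truncation, and a 10% limit on standardized differences. SAP 7.1.3 adds that "Baseline characteristics (before and after IPTW weighting) will be compared between patients treated with warfarin and patients treated with apixaban", and SAP 7.1.4 does the same for categorical variables.
- **Cox model.** SAP 7.1.6 uses robust variance and provides a fallback: "If not balanced, the unbalanced variable will be also included to the model".
- **Kaplan-Meier.** SAP 7.1.5 says of the weighted curves: "The log-rank test will be used for comparison between two curves".
- **Quality control.** Protocol 9.8 says of the analysis contractor that "they will conduct code review of all modules of program, descriptive statistics review of all variables".

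**The concern.** A stabilized weight needs two quantities: the patient's own treatment (0 or 1) and the marginal probability of treatment. The printed equation has one symbol, defined as the second. Read as defined, it adds the apixaban weight and the warfarin weight together and gives the sum to every patient. The result depends on PS alone, so it cannot make the arms comparable. It also disagrees with the sentence before it, which gives each arm its own constant.

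These weights feed every balanced-cohort comparison in SAP 7.2.3, including major bleeding and stroke/SE. If the equation were coded literally and not corrected at source, the Cox fallback would act on the hazard ratio. No fallback is stated for the weighted Kaplan-Meier curves, the log-rank test or the incidence rates. Those would keep roughly the crude confounding.

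**Working it through.** The plan attaches no numerical result to the formula, so there is no figure to reproduce. The check is algebra, then illustration.

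**1. Algebra (no assumed data).** At a given PS the unweighted odds of apixaban to warfarin are PS/(1−PS). The printed weight w(PS) is the same in both arms, so the weighted odds are PS·w/[(1−PS)·w] = PS/(1−PS), unchanged. The weight described in words gives PS·(p/PS) to (1−PS)·(1−p)/(1−PS), that is p/(1−p) at every PS, which is balance.

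**2. Size of the weights.** Protocol 9.5 reports for the previous study (CER3) that "15,902 patients on warfarin, 22,336 patients on apixaban were eligible for the analysis". Hence p = 22,336/(22,336 + 15,902) = 22,336/38,238 = 0.584.

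| PS | Words: apixaban | Words: warfarin | Printed: both arms |
|---|---|---|---|
| 0.10 | 0.584/0.10 = 5.84 | 0.416/0.90 = 0.46 | 6.30 |
| 0.90 | 0.584/0.90 = 0.65 | 0.416/0.10 = 4.16 | 4.81 |

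**3. Two-stratum example.** All PS and confounder values are assumed, with no true treatment effect. Confounder prevalence is 40%, PS is 0.45 if present and 0.65 if absent, and the confounder doubles the event rate. The unweighted warfarin rate is set to the 3.77%/year of SAP 7.1.9.

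- p = 0.4×0.45 + 0.6×0.65 = 0.57.
- Printed weights: 0.57/0.45 + 0.43/0.55 = 2.05, and 0.57/0.65 + 0.43/0.35 = 2.11.
- Rate in an arm with confounder prevalence q is r(1+q). Unweighted warfarin q = 0.4×0.55/0.43 = 0.512, so r = 37.7/1.512 = 24.9 per 1,000 person-years.
- Standardized difference (SMD) = (q_A − q_W)/√{[q_A(1−q_A) + q_W(1−q_W)]/2}.

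| | q apixaban | q warfarin | SMD | Rates per 1,000 person-years | Ratio | Mean weight |
|---|---|---|---|---|---|---|
| Unweighted | 0.316 | 0.512 | −0.41 | 32.8 vs 37.7 | 0.87 | – |
| Printed | 0.310 | 0.505 | −0.40 | 32.7 vs 37.5 | 0.87 | 2.08 |
| Correct | 0.400 | 0.400 | 0 | 34.9 vs 34.9 | 1.00 | 1.00 |

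The arm odds in the two strata are 0.82 and 1.86, both unweighted and with the printed weight. With the correct weight both are 0.57/0.43 = 1.33.

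**4. Range.** With p = 0.584, prevalence 40% and a doubled rate:

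| PS gap (points) | SMD | Rate ratio, unweighted and printed | Mean printed weight |
|---|---|---|---|
| 5 | −0.10 | 0.97 | 2.00 |
| 10 | −0.20 | 0.93 | 2.02 |
| 20 | −0.41 | 0.87 | 2.08 |
| 40 | −0.87 | 0.76 | 2.38 |

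A milder case (PS 0.50/0.60, rate ×1.5) gives ratio 0.96 and SMD −0.20, unweighted and printed alike. Extreme scores make the printed weight worse than none: with prevalence 20% and PS 0.10/0.70, the SMD is −1.51 against −1.06 unweighted, and the ratio 0.65 against 0.72.

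**5. Simulation with several confounders.** Assumptions: 400,000 patients, three standard normal confounders, PS log-odds intercept 0.3, coefficients 0.8, −0.6 and 0.4 scaled by 0.3, 0.5, 0.7 and 1.0. The largest absolute SMD is 0.23, 0.38, 0.52, 0.68 unweighted; 0.25, 0.44, 0.67, 1.08 with the printed weight; and at most 0.01 with the correct weight.

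**6. The other reading of Z.** If Z is taken as a 0/1 indicator, against its legend, the equation becomes the ordinary unstabilized weight, 1/PS or 1/(1−PS). That balances the arms, but the mean weight is 2.00 rather than 1.

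**The case against.** The strongest reply is that the right weight is already described in words in the same section, and the SAP cites a reference on stabilized weights, so only the notation is faulty. The equation has a capital Z and the legend a lower-case z, which PDF conversion may have altered. If Z were the usual indicator, the weights would balance the cohorts. Three planned checks (weight distribution, standardized differences before and after, code review) would probably expose a literal implementation. The Cox fallback would then adjust for what remained unbalanced, so the rate ratios above do not describe the primary hazard ratio.

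Much of this stands. The intent can be recovered. In the two-stratum examples, adjusting for the single confounder would remove the bias from the hazard ratio wherever the 10% limit is exceeded; the 5-point gap sits at that limit. The ratios therefore apply to the unadjusted weighted outputs.

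Three things do not go away:

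- Neither reading of Z gives the stabilized weight. One does not balance, and the other is not stabilized and contradicts the legend.
- The balance check would miss the indicator reading, because that weight does balance. If the log-rank test then treated weights near 2 as patient counts (an assumption), its statistic would grow by √2. The effective critical value would be 1.96/√2 = 1.39, and a nominal 5% test would run at about 17%.
- Truncation does not rescue the printed form, because a truncated function of PS is still a function of PS. In a second simulation (1,000,000 patients, treated share 0.584, one normal and one binary covariate with log-odds coefficient 1.0), the SMD of the normal covariate was 0.88 unweighted, 1.41 printed and 1.23 after truncation at the 5th and 95th percentiles.

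**Conclusion.** The concern holds. The equation is wrong as printed: it conflicts with its own introductory sentence, and no other section corrects it. That a literal implementation fails to balance follows from algebra and needs no assumption about the data.

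The size of the resulting bias does rest on assumptions, since the documents give no PS distribution or baseline imbalance. Over PS gaps of 5 to 40 points, a true ratio of 1.00 would appear as 0.97 to 0.76, the same as with no weighting. With extreme scores, imbalance would be larger than in the crude data.

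The practical risk is limited, because the intent is recoverable and the planned checks would probably catch the error. It should still be fixed: the equation specifies the core adjustment for both primary endpoints, and code review needs a correct specification to review against.

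**What to change.** Replace the equation in SAP 7.1.2 with

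`SW_i = T_i*p/PS_i + (1-T_i)*(1-p)/(1-PS_i)`

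where T_i = 1 for apixaban and 0 for warfarin, PS_i is the estimated probability of apixaban, and p is the marginal proportion on apixaban.

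Add a check that the mean weight is about 1 in each arm. It detects both misreadings. In the two-stratum example the printed formula averages about 2.1 in each arm. The unstabilized weight averages 1/p and 1/(1−p), which at p = 0.584 is 1/0.584 = 1.71 for apixaban and 1/0.416 = 2.40 for warfarin.

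Correct the cross-reference to 7.1.2.1 so that it points to 7.1.1.

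A secondary and minor point: SAP 7.1.6 states robust variance for the Cox model only. Either base the weighted p-value on the robust Cox test or specify a log-rank test with robust variance.

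The cost is one or two lines of SAP text before programming, with no effect on data or timeline.
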